10.8.5. Laboratory Assessments

The laboratory safety analyses (haematology and clinical chemistry) will be performed by local laboratories at the timepoints shown in [Table 1](#).

Sampling methods and procedures will be in accordance with local routine care.

The following laboratory safety parameters will be analysed:

Table 4: Laboratory Safety Parameters

Category	Laboratory Parameter
Haematology	Haemoglobin, RBC, Red Blood Cell Distribution Width (RDW), Haematocrit, Mean cell volume (MCV), Mean cell haemoglobin (MCH), Mean cell haemoglobin concentration (MCHC), Platelet count, WBC and differential counts (absolute and percentage): Neutrophils, Lymphocytes, Monocytes, Eosinophils, Basophils, Prothrombin Time International Normalised Ratio (PT-INR)

Category	Laboratory Parameter
Clinical chemistry	Aspartate Aminotransferase (AST), Alanine Aminotransferase (ALT), Gamma Glutamyl Transpeptidase (GGT), Alkaline Phosphatase, Bilirubin, Urea, S-Creatinine, Potassium, Sodium, Calcium, Chloride, Phosphate, Total protein, Albumin, C-Reactive Protein (CRP), and Glucose (non-fasting)

All results will be recorded in the eCRF and will be assessed as ‘clinically significant’ or ‘not clinically significant’. Clinically significant findings identified at Baseline (Visit 1) should be recorded as medical history. Clinically significant findings not present at Baseline (Visit 1) should be reported as AEs.

10.8.5.1. PK assessment (Only for Italy)

The subjects enrolled in Italy will have Visits 1 - 6 scheduled for an on-treatment week during the allowed window of +/- 4 weeks. On the day of the visit, IMP dosing will be conducted at the site.

Two serum samples for analysis of GM-CSF will be collected at each of these visits. The first sample will be taken just prior to inhalation of molgramostim. The second sample will be taken 2 hours post dosing, (+/- 10 minutes). Samples will be shipped to a central laboratory for analysis. Further description of sample collection, processing, shipment and analyzing will be available in the laboratory manual. Timing of dose on the day before and on the day of sampling will be recorded in the eCRF.

10.8.5.2. Pregnancy Screen

A serum pregnancy test will be performed for female subjects of child-bearing potential at each visit. For subjects who have a gap between completion of IMPALA and Baseline (Visit 1), a urine pregnancy test will also be performed before dosing at Baseline (Visit 1) in order to immediately confirm that the subject is not pregnant. If treatment is not dispensed at Baseline (Visit 1), the urine pregnancy test will be performed at start of treatment. Female subjects of child-bearing potential will be instructed to conduct a monthly urine pregnancy test at home.

10.8.5.3. Computed Tomography (CT)

A CT scan is not required as part of this trial. Only if a CT scan is performed according to clinical practice or medical need, e.g. in case of a clinical deterioration, the results will be recorded in the eCRF as improved / worsened / no change / data missing – impossible to evaluate, compared to the last evaluation in IMPALA.

10.9. Adverse and Serious Adverse Events

10.9.1. Definitions of Adverse Events

10.9.1.1. Adverse Event (AE)

Any untoward medical occurrence in a patient or clinical trial subject administered a medicinal product and which does not necessarily have a causal relationship with this treatment.

An AE can therefore be any unfavourable and unintended sign (including an abnormal laboratory finding), symptom, or disease temporally associated with the use of an IMP, whether or not considered related to the IMP.

10.9.1.2. Serious Adverse Event (SAE)

Any untoward medicinal occurrence or effect that at any dose:

- Results in death
- Is life-threatening
- Requires hospitalisation or prolongation of existing hospitalisation
- Results in persistent or significant disability or incapacity
- Is a congenital abnormality or birth defect
- May jeopardise the subject or may require medical intervention to prevent one or more of the outcomes listed above (Important Medical Events).

Life-threatening in the definition of an SAE or serious adverse reaction refers to an event in which the subject was at risk of death at the time of event; it does not refer to an event which hypothetically might have caused death if it was more severe.

For important medical events, medical judgement should be exercised in deciding whether an AE/reaction is serious.

The severity of an adverse reaction is largely determined by the outcome of the medical occurrence. An adverse reaction should only be termed "serious" if hospitalisation did in fact take place as a result of it. As a rule, hospitalisation is the admission to a hospital with at least one overnight stay.

The presentation of a patient in the emergency room (casualty center, health care center) alone without subsequent in-patient admission does not yet fulfill the criterion hospitalisation. However, it should be confirmed whether any of the other criteria mentioned above justifies an adverse reaction being classified as "serious" or at least "medically significant."

If the Investigator becomes aware of an SAE with a reasonable relationship to the IMP after the subject has left the trial, this SAE must also be reported (post-trial event).

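### Protocol 10.9.1.2 says a reaction is serious only if hospitalisation took place, which contradicts its own six alternative criteria; reconcile the text and recheck ADRs coded non-serious before database lock.

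*Protocol*

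**What the plan says.** Protocol 10.9.1.2 defines an SAE by a list of six alternatives. Five are "Results in death", "Is life-threatening", "Requires hospitalisation or prolongation of existing hospitalisation", "Results in persistent or significant disability or incapacity" and "Is a congenital abnormality or birth defect". The sixth is the category of important medical events, for which the section adds: "For important medical events, medical judgement should be exercised in deciding whether an AE/reaction is serious".

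A later paragraph of the same section states: "An adverse reaction should only be termed 'serious' if hospitalisation did in fact take place as a result of it". It then explains that hospitalisation means, as a rule, an admission with at least one overnight stay. The paragraph after that says that attending an emergency room or similar facility without being admitted does not meet the hospitalisation criterion. It asks the site to check whether one of the other listed criteria makes the reaction serious, or failing that at least medically significant.

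SAEs are part of the primary endpoint (Protocol 5.3.1 and 11.1). SAP 7.1 lists serious and non-serious adverse events as separate primary categories, next to all AEs, ADRs and AEs leading to treatment discontinuation.

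**The concern.** The list makes hospitalisation one sufficient condition among six. The later sentence, with its unqualified only, makes it a necessary condition. Both rules cannot hold.

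The closing phrase about medical significance adds a second ambiguity. It can be read as a tier below serious, although important medical events are themselves on the SAE list.

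Three things depend on the seriousness flag:

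- **Primary endpoint tables.** It decides whether an event is tabulated as serious or non-serious.
- **Expedited reporting by the site.** Protocol 10.9.3.1 requires SAEs to reach the sponsor within 24 hours.
- **SUSAR status.** Seriousness is one of three conditions in Protocol 10.9.1.2.1, and SUSAR status starts the 7-day and 15-day clocks in 10.9.3.2.

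Because the sentence speaks of an adverse reaction, its literal effect falls on drug-related events. Those matter most in a trial whose primary objective is long-term safety.

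**Working it through.** No figure in the plan bears on the definition, so the check compares the texts.

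**Step 1: the list against the sentence.**

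| Criterion in the list | Admission needed under the list? | Effect of the sentence read literally |
|---|---|---|
| Death | No | Contradicted |
| Life-threatening | No | Contradicted |
| Hospitalisation or its prolongation | Yes, or a longer stay | Narrowed: prolongation is not mentioned |
| Disability or incapacity | No | Contradicted |
| Congenital abnormality or birth defect | No | Contradicted |
| Important medical event | No, medical judgement | Contradicted |

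Five of the six criteria are contradicted outright and one is narrowed.

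**Step 2: other protocol text.** Section 10.9.3.5 requires stillbirth, birth defect and certain other pregnancy outcomes to be reported as SAEs, with no admission condition. Section 10.9.2.5 refers to laboratory or vital-sign findings that meet the SAE criteria, in the plural. Both fit the list and not the sentence.

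**Step 3: where a misclassified event would go.** Take a reaction judged possibly or probably related, life-threatening, and managed without admission. If it is coded non-serious:

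- It still counts as an AE and as an ADR (SAP 7.1).
- If treatment emergent, it leaves SAP Tables 14.3.1.7 to 14.3.1.10 (serious) and enters Tables 14.3.1.11 to 14.3.1.15 (non-serious).
- The ADR tables, 14.3.1.16 to 14.3.1.19, are split by severity, relationship and outcome but not by seriousness, so they would not show the shift.
- No 24-hour report is triggered, and the event cannot become a SUSAR.

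**Step 4: would planned checks catch it?** Before database closure, Protocol 14.1 reconciles SAEs between the safety and trial databases. An event never flagged as serious is in neither SAE set, so that reconciliation would not find it. Protocol 10.9.3.3 defines no adverse events of special interest, so there is no second route to expedited attention there.

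**Step 5: scale.** The number of affected events cannot be derived. As a unit of measure only, SAP 3.2 gives 60 enrolled subjects, 55 of them on treatment at termination. SAE tables use the safety analysis set (subjects exposed in the trial), which on these figures is between 55 and 60. One subject whose only SAE is coded non-serious changes overall incidence by 1/60 = 1.7 to 1/55 = 1.8 percentage points.

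**The case against.** The best defence is context. The sentence is followed at once by an explanation of what hospitalisation means. The next paragraph says that attendance without admission fails that one criterion and sends the site back to the others. On this view the sentence only separates an admission that happened from one that might have happened, much as the preceding text does for life-threatening events. The literal reading would make a death outside hospital non-serious, which nobody can have intended. The referral back also covers casualty and health care centres, so it reaches many of the reactions at issue. The site must state the seriousness criteria in the initial SAE report, and a trial-specific SAE procedure and a Safety Management Plan exist, whose contents are not available here.

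Much of this stands. It makes a drafting slip the likely explanation and lowers the practical risk. It does not remove the conflict. The sentence is not limited to the hospitalisation criterion, the referral back is written for attendance without admission, and a reaction managed with no such visit is not expressly covered. The phrase about medical significance may be a loose reference to important medical events; the documents do not settle its meaning, which is itself a reason to delete it.

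A reader might infer that sites would fail to report such reactions, or that the SAE count is already too low. The documents do not support either inference: a site reading the whole section could apply the list correctly, and no misclassified event is shown. A reader might also infer that all SAEs are exposed. The sentence concerns reactions, so unrelated SAEs are outside its literal reach.

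**Conclusion.** The contradiction is definite and is in the current text: five criteria contradicted and one narrowed. The consequence is possible, not established. A site applying the sentence literally might code a drug-related serious reaction without admission as non-serious, which would shift it between two primary categories and out of expedited reporting. It would not vanish from the AE or ADR counts.

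The size cannot be estimated. The 1.7 to 1.8 percentage points per subject is a scale, and it assumes that the enrolment and treatment figures in SAP 3.2 bound the safety analysis set and that the subject has no other SAE. The conclusion also assumes that no site document outside the protocol and SAP already corrects the sentence. Given the low cost, the text should be corrected and the coding checked.

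**What to change.** **Protocol text.** Reconcile the passages by stating that:

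- the sentence and the overnight-stay explanation apply to the hospitalisation criterion only, and the overnight stay remains a general rule rather than an absolute;
- prolongation of an existing hospitalisation also meets that criterion;
- any one of the six criteria is sufficient, whether or not the subject was admitted.

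Delete the closing phrase that offers medical significance as a fallback to serious.

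**Data already collected.** SAP 3.2 says that the trial has been discontinued and that treatment continued only until the end of 2020, so rewording alone would not correct existing records. Before database lock, check ADRs coded non-serious against all six criteria, using the ADR listing (16.2.7.3) as the starting point. Raise queries where a criterion appears to be met, so that any change is made at the site as Protocol 14.1 requires. State in the clinical trial report which rule was used and how many events changed.

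**Cost.** A few sentences with a site note, handled through the documented amendment that Protocol 12.5 requires, and a small amount of extra data review. The SAE count may rise slightly. If an amendment is no longer practical, the data check and the statement in the report can still be done.

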10.9.1.2.1. Suspected Unexpected Serious Adverse Reaction (SUSAR)

A SUSAR is an AE which

- Has a reasonable possibility of causal relationship to an IMP
- Is serious, and
- Is unexpected

Therefore, due to the nature and/or severity of the adverse reaction, a SUSAR is not consistent with the applicable product information (i.e. the reference safety information in the IB) for the IMP used in this trial.

10.9.2. Recording Adverse Events

All trial subjects will be carefully monitored for the occurrence of AEs during the trial period from Baseline to the last visit. The investigator will collect AEs using a non-leading question such as “have you experienced any new health problems or worsening of existing conditions” as well as reporting events directly observed or spontaneously volunteered by subjects.

Clearly related signs, symptoms and abnormal diagnostic procedure results should be grouped together and reported as a single diagnosis or syndrome whenever possible.

All AEs including but not limited to events reported by the subject, or reported in answer to an open question by the investigator or member of this team, which fall into any of the above definitions must be recorded as an AE in the eCRF and should include the following information:

- Brief description of the event (diagnosis)
- Start date (and time, if relevant)
- Stop date (and time, if relevant) (or resolution)
- Severity
- Action taken regarding trial drug
- Opinion on causality
- Seriousness
- Outcome.

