- Number of AEs, serious adverse events (SAEs), adverse drug reactions (ADRs), and AEs leading to treatment discontinuation during the trial.

Secondary Endpoints:

- Alveolar-arterial oxygen difference ((A-a)DO₂) during the trial.
- 6-minute walking distance (6MWD) during the trial.

- St Georges Respiratory Questionnaire (SGRQ) total score during the trial.
- Frequency of WLL during the trial.
- Diffusion Capacity of the Lung for Carbon Monoxide (DLCO), Forced Expiratory Volume in one second (FEV₁), and Forced Vital Capacity (FVC) during the trial, all expressed as percent predicted.
- Arterial oxygen tension (PaO₂) and disease severity scores (DSS) during the trial.
- Need for oxygen supplement therapy during the trial.
- Number of subjects not requiring treatment for aPAP and time off treatment after discontinuation of inhaled molgramostim

Exploratory Endpoints:

- GM-CSF levels before and 2 hours after dosing

Methods of Assessment:

Lung function variables – DLCO and spirometry (FEV₁ and FVC) will be done in accordance with European Respiratory Society/American Thoracic Society (ERS/ATS) guidance using local equipment. For spirometry percent of predicted values will be calculated centrally using standard equations.

6-minute walking test (6MWT) – will be performed in accordance with European Respiratory Society/American Thoracic Society (ERS/ATS) guidance. Borg CR10 scale will be used to assess dyspnoea before and after the test.

Quality of Life score – SGRQ

Laboratory analyses – Local laboratories will be used for analysis of haematology, clinical chemistry and pregnancy testing.

(For Italy only: samples will be collected for pharmacokinetic (PK) analysis at Visit 1-6, pre-dose and 2 hours post dosing)

Statistical methods:

Data from the trial will be analysed descriptively. Data from the trial is planned to be combined with relevant data from the IMPALA trial; these combined analyses will be reported separately.

Table 1: Study Flow Chart

Visit	Visit 1	Visit 2	Visit 3	Visit 4	Visit 5	Visit 6	Visit 7	FU TC	Unscheduled
	Baseline ^a	Month 6	Month 12	Month 18	Month 24	Month 30	Month 36	2 wks after trial completion	
Time	0	Week 26	Week 52	Week 78	Week 104	Week 130	Week 156		
Visit Window	N/A	± 4wks	± 4 wks	± 4 wks	± 4 wks	± 4 wks	± 4 wks	+ 1 wk	
Informed consent	X								
Eligibility criteria	X								
Demographics	X								
Concomitant medication	X	X	X	X	X	X	X		X
WLL information ^b	X	X	X	X	X	X	X		X

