6.1.1. Trial Period

The first patient will be included in the trial in Q1 2018 and the expected end of trial is in Q1 2021. Should the product not have obtained marketing authorization at this date, the trial will be amended with an extension of one year at a time to ensure adequate treatment options for subjects in the trial who still are in need of treatment with inhaled molgramostim. Trial completion, defined as the date of the Clinical Trial Report, is expected 1 year after trial end.

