10.6. Follow-up Telephone Visit

The site should call the subject approximately one week after the subject has completed the last trial visit in order to assess whether any new AEs have occurred after the visit, and to obtain follow-up information on any AE ongoing at the last trial visit.

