10.8.1. Adverse Events

Any AEs will be reported at every visit from Baseline (Visit 1) to the completion of the trial. Subjects will be encouraged to contact the clinic in between visits if they experience AEs or have any concerns. For further information of definitions and reporting of AEs and SAEs, see Section 10.9.

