10.9.3. Reporting Adverse Events

10.9.3.1. Serious Adverse Event (SAE) Reporting Procedure

The investigator is responsible for ensuring that all SAEs are reported to the sponsor immediately, using a trial-specific SAE form, but in any event no later than 24 hours of any site staff becoming aware of the event from the time the informed consent has been signed, up to Day 30 after the last visit. Reporting of SAEs will also be described in a trial-specific procedure.

After that period of time only serious adverse reactions (events related to trial medication) have to be reported. SAEs occurring to a patient after the patient has completed the clinical trial and for which a reasonable possibility of a causal relationship is assessed by the Investigator, must be reported by the Investigator to Premier Research regardless of the time that has elapsed (post-trial events). The SAE form has to be completed in English.

Initial reports should be followed as soon as possible by detailed written reports. The initial and follow-up reports should identify subjects by unique code numbers assigned in the trial. The subjects' names, personal identification numbers, and/or addresses must not be included. The following information is **mandatory** for the initial report:

- Subject trial ID
- Trial treatment (blinded, if applicable)
- Start date (time, if relevant) of the trial treatment
- Brief description of the event (diagnosis)
- Start date (time, if relevant) of the event
- Seriousness criteria
- Causality assessment.

For reported deaths, the investigator should supply the sponsor and the IEC/IRB (if applicable) with any additional requested information (e.g. autopsy reports and terminal medical reports).

The Investigator must contact Premier Research by email or fax directly to Premier Research Pharmacovigilance and Device Safety in case of all SAEs **within 24 hours after awareness of the event**.

SAE REPORTING CONTACT DETAILS

Company: Premier Research

Department: Pharmacovigilance and Device Safety (PVDS)

E-mail: [contact]

[contact]

Note: If there is local legislation requiring investigators to report AEs to the Competent Authority or the IEC/IRB, the investigator should also comply with this legislation. If any such reporting is planned, this must be stated in the SAE report, and once the reporting has been performed, a copy of the reporting documentation must be enclosed with the SAE-Follow-Up report to the sponsor.

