8.1.1 Analysis and Presentation of Safety Parameters

8.1.2 Adverse Events

All adverse events (AEs) occurring after informed consent will be reported in the eCRF. AEs will be coded using the Medical Dictionary for Regulatory Activities (MedDRA) version 21.0.

Adverse events are considered treatment emergent if the onset of the events is on or after the first exposure date of IMP in this trial and until (estimated) last drug date + 7 days. Last drug date is defined as last kit date + 21 days or end of trial date whatever comes first. Only treatment emergent events will be included in the safety summaries.

Possible or probable related AE's are defined as ADRs.

Adverse events will be presented as described in section 7.1.

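### The protocol contradicts itself on when the final adverse event contact takes place, and serious events reported after the SAP's 7-day window reach listings but no summary table

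*Protocol*

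**What the plan says.** The primary endpoint is the number of AEs, SAEs, adverse drug reactions and AEs leading to treatment discontinuation (Protocol 5.3.1 and 11.1). Several places bear on when AE collection ends:

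- Protocol 10.9.2: "All trial subjects will be carefully monitored for the occurrence of AEs during the trial period from Baseline to the last visit".
- Protocol 10.6: "The site should call the subject approximately one week after the subject has completed the last trial visit". The stated purpose includes asking about new AEs since that visit.
- Protocol Table 1, repeated in the SAP: the follow-up call is headed "2 wks after trial completion", has a window of +1 week, and has the AE row marked.
- Protocol 10.8.1: "Any AEs will be reported at every visit from Baseline (Visit 1) to the completion of the trial". Section 6.1.1 adds: "Trial completion, defined as the date of the Clinical Trial Report, is expected 1 year after trial end".

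SAEs have their own rule. Protocol 10.9.3.1 requires reporting "from the time the informed consent has been signed, up to Day 30 after the last visit". After that, only serious events judged related to treatment must be reported.

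SAP 8.1.2 treats an event as treatment emergent from first exposure in this trial "until (estimated) last drug date + 7 days". The last drug date is the earlier of last kit date plus 21 days and the end of trial date. SAP 5.1 takes the end of trial date from the completion or discontinuation date in the eCRF. Only treatment-emergent events enter the safety summaries. SAE Tables 14.3.1.7 to 14.3.1.10 are titled that way, while Listings 16.2.7.1 (AEs) and 16.2.7.2 (SAEs) cover all subjects.

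**The concern.** There are two separate issues, and both touch the primary endpoint.

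First, 10.6 and Table 1 describe the same telephone call at different times, and 10.9.2 reads as if collection had already stopped. Sites following different sections would observe subjects for different lengths of time after the last visit, while the SAP counts the same seven days for everyone. If a call comes before those seven days are over, a non-serious event in the remainder may never be recorded.

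Second, the protocol asks for all SAEs to Day 30, but the SAP summarises only those inside its window. A death or SAE shortly after the window, even one judged related to treatment, would be reported and then left out of every count and rate.

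**Working it through.** The plan has no sample size or error rate to reproduce, because the trial is descriptive. The check is a day count with day 0 as the last visit.

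**Inputs**

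- Call day *c*: about 7 (Protocol 10.6), or 14 to 21 (Table 1). For Table 1, I take trial completion to mean the subject's own last visit. The definition in 6.1.1 would put the call about a year after trial end, which cannot be meant.
- SAP window: ends at day *d* + 7, where *d* is the estimated last drug date relative to the last visit (SAP 8.1.2).
- SAE reporting: to day 30 (Protocol 10.9.3.1).
- Subjects: 60 enrolled, 55 of them on treatment at termination (SAP 3.2).

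**Call timing.** About day 7 and days 14 to 21 do not overlap, so the two instructions cannot both be met by one call.

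**Coverage of the SAP window when *d* = 0.** Days covered = min(*c*, 7).

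| Call | Days covered, of 7 | Days collected beyond the window |
|---|---|---|
| 10.6, day 5 | 5 | 0 |
| 10.6, day 7 | 7 | 0 |
| 10.6, day 8 | 7 | 1 |
| Table 1, day 14 | 7 | 7 |
| Table 1, day 21 | 7 | 14 |

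Only a call on the early side of one week leaves a gap. Days 5 and 8 are my illustrations of an approximate week.

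**SAE days reported but not summarised.** Gap = 30 − max(0, *d* + 7).

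- *d* = 0: 30 − 7 = 23 days, and 23/30 = 77%.
- *d* = −3: 30 − 4 = 26 days.
- *d* = −7 or earlier: 30 − 0 = 30 days.
- *d* = +7, possible only if the eCRF completion date is entered at the one-week call and last kit date plus 21 days is no earlier: 30 − 14 = 16 days. The window would then run to day 14.

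**Scale**

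- Against the planned three years: 7/(3 × 365.25) = 0.6%, and 23/(3 × 365.25) = 2.1%. Early termination makes these shares larger for subjects followed for less time.
- Person-time in the 23 days: 55 × 23/365.25 = 3.5 person-years, or 60 × 23/365.25 = 3.8.
- The documents give no event rate, so the number of events affected cannot be computed.

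**The case against.** The strongest reply is that these provisions add to one another. Both 10.6 and Table 1 require a call that asks about AEs, and 10.9.2 does not forbid it. A reader might infer from 10.9.2 that none of the seven days is collected, but that would need a site to skip a call required in two places. This part of the reply stands.

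An approximate week can also fall after day 7, in which case the window is fully covered. On the base case, 10.6 roughly matches the SAP. This stands too, and it limits the gap to early calls.

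A reader might also see the Day-30 rule as a further contradiction. It is not one: an SAE reporting period may properly run longer than general AE collection.

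Nor do late SAEs go unreported. The SAP restricts summaries, not listings; Protocol 11 says listings show all recorded data; and Protocol 14.1 reconciles SAEs between the safety and trial databases before closure. With 60 subjects, the SAE listing can be read line by line. What remains is that a listing gives no count or rate, and the endpoint is a count.

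It can be added that under alternating weeks some subjects attend in an off-treatment week. That affects true exposure but not the counting window, which rests on an estimated last drug date.

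Finally, treatment was to run only to the end of 2020 and SAP version 3.0 is dated January 2021. Rewording the protocol cannot recover AEs that were not collected. That is correct, and the fix allows for it.

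**Conclusion.** The point holds in two limited parts.

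The timing of the last AE contact is contradictory in current text: the last visit in 10.9.2, about one week later in 10.6, and two to three weeks later in Table 1. The consequence is that an early call under 10.6 can leave the last day or two of the SAP window uncollected for subjects whose estimated last drug date is at or near the last visit. The effect is probably small. For subjects who stopped well before, the window had closed by the last visit.

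SAEs and deaths after the window, up to Day 30, enter no summary table. This covers 23 of 30 days if the last drug date equals the last visit, and up to all 30 if it is earlier. The documents do not fix the figure of 23, because the end of trial date is not tied to the last visit and the last kit date is undefined.

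The documents do not support a claim that the primary endpoint is materially distorted. The days are few, the trial makes no formal comparison, and no event rate is given. The point is worth correcting because it concerns the primary endpoint, the remedy is cheap, and SAP 3.2 says the data will go into the safety evaluation and a possible marketing application.

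**What to change.** **Protocol.** Give 10.6, 10.9.2 and Table 1 one end of AE collection, no earlier than the end of the SAP window, and bring the wording of 10.8.1 into line. Leave the Day-30 SAE reporting period in 10.9.3.1 as it is. Where collection is already finished, state in the clinical trial report which call timing was used.

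**SAP.** Add one row to Table 14.3.1.1, or one short table, counting SAEs and deaths (events and subjects) with onset after the treatment-emergent window and up to Day 30 after the last visit. Keep it apart from the treatment-emergent rows and label the period. For subjects who stopped treatment early, it will also take in off-treatment follow-up.

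**Cost.** A few lines of wording and one extra row or table, built from data already required. The downside is that the overall SAE total may look slightly less favourable.
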